**Official Title: Intraoperative Positive End-Expiratory Pressure Setting Guided by
Esophageal Pressure Measurement in Patients Undergoing
Laparoscopic Gynecologic Surgery**

**Brief Title: Intraoperative PEEP Setting During Laparoscopic Gynecologic
Surgery**

Principal Investigator: [name]

**Affiliation: Department of Anesthesiology, Faculty of Medicine Siriraj
Hospital, Mahidol University, Thailand**

NCT Number: N/A

Updated: August 17, 2017

Intraoperative Positive End-Expiratory Pressure Setting Guided By Esophageal Pressure Measurement in Patients Undergoing Laparoscopic Gynecologic Surgery

Introduction

Nowadays, laparoscopic surgery has been substantially performed worldwide. It is considered as minimally invasive procedure with numerous advantages compared with open surgery including less postoperative pain, faster recovery, shorter length of hospital stay and less overall medical cost⁽¹⁾. The creation of pneumoperitoneum (PP) during laparoscopic surgery, however, can have significant effects on the respiratory system. The rise in intraabdominal pressure (IAP) causes cephalic displacement and stiffness of the diaphragm resulting in a decrease in the compliance of the respiratory system (C_{RS}) and of the chest wall (C_{CW})⁽²⁻⁴⁾ as well as an increase in pleural pressure (P_{pl}) likely due to thoracoabdominal transmission of IAP. Combine with a decrease in respiratory muscle tone following general anesthesia⁽⁵⁾, the vital capacity and the functional residual capacity (FRC) are declined⁽²⁾. There also atelectasis formation resulted from airway closure (compressive atelectasis) and absorption of gas trapped distal to occluded airways (absorption atelectasis)⁽⁶⁾. All of these changes potentially lead to an increase in dead space ventilation as well as shunt and subsequently impair oxygenation⁽⁵⁾. This pathophysiology may put patients at risk of postoperative pulmonary complications (PPCs) such as respiratory infection, respiratory failure, reintubation or prolonged mechanical ventilation and possibly increase mortality^(7, 8).

Therefore, intraoperative mechanical ventilation has an important role in respiratory management during laparoscopic surgery⁽⁹⁾. Setting of positive end-expiratory pressure

(PEEP) has been shown to attenuate the derangement of respiratory mechanics and the impairment in oxygenation caused by PP⁽¹⁰⁻¹⁵⁾. In addition, the application of PEEP as a part of intraoperative protective mechanical ventilation may be associated with a decrease in PPCs following laparoscopic surgery⁽¹⁶⁾. Nevertheless, there is no consensus on the optimal PEEP level and the best method to set PEEP during laparoscopic surgery⁽⁹⁾. In patients with acute respiratory distress syndrome (ARDS), Talmor et al⁽¹⁷⁾ demonstrated that mechanical ventilation with PEEP set according to P_{pl} measured by using esophageal balloon catheter significantly had beneficial effects in terms of oxygenation, C_{RS} and possible mortality. With PEEP set according to this method, the transpulmonary pressure (P_{TP}), which is the difference between the pressure inside alveoli or PEEP and the pressure outside or P_{pl} , is constantly maintained positive during expiration. Consequently, it helps to prevent the formation of atelectasis as well as to recruit the collapsed alveoli and, thus, to improve oxygenation. To date, there is limited data regarding the use of esophageal balloon catheter to set PEEP in mechanically ventilated patients undergoing laparoscopic surgery. Therefore, the aim of this study is to determine whether PEEP titration guided by P_{pl} measurement during laparoscopic surgery would improve pulmonary function in term of oxygenation as well as other parameters such as compliance and alveolar dead space.

Material and Method

Patient population

This randomized controlled trial includes patients with age of equal or more than 18 years old undergoing laparoscopic gynecologic surgery with anticipated surgical duration of more than 2 hours. Patients with the American Society of Anesthesiologists (ASA) physical status of equal or more than 3, those with significant cardiovascular or respiratory diseases, those with significant pathological lesion in pharynx and esophagus that preclude placement of esophageal balloon catheter, those with contraindications for PEEP titration such as increased intracranial pressure or unstable hemodynamic, those with arrhythmias, those who refuse to provide written informed consent, and those undergoing surgery with duration of less than 2 hours are excluded from the study. Informed consent is obtained from all included patients.

Study protocol

Prior to induction of general anesthesia, standard monitoring including non-invasive blood pressure measurement, pulse oxymetry, electrocardiogram, capnometry and peripheral nerve stimulator (TOF-Watch, Organon, Ireland), which is applied to the temporal branch of facial nerve and recorded response of the orbicularis oculi, as well as non-invasive cardiac output measurement with the pulse wave transit time technology (Vismo, Nihon Kohden, Japan) are applied to all patients. General anesthesia is induced with 1.5-2 mg/kg of propofol, 2 mcg/kg of fentanyl and 0.6 mg/kg of rocuronium and then trachea is intubated with proper size of endotracheal cuff tube. After induction and intubation, arterial catheter is inserted at radial artery for repeated arterial blood gas sampling. Anesthesia is maintained with 1 minimal alveolar concentration (MAC) of

desflurane and supplemental doses of morphine and rocuronium as required. Train-of-four (TOF) stimulation with peripheral nerve stimulator is kept between 1 and 2 twitches to facilitate relaxation. In case of hemodynamic instability, fluid as well as inotropes and vasopressors are administered according to discretion of anesthesia staff. The surgery is initially started in the lithotomy position and then in the 45-degree Trendelenburg position at the initiation of PP. PP is created by intraabdominal insufflation of carbon dioxide (CO₂) and IAP is maintained at 12 to 15 mm Hg during PP. At the end of the surgery, reversal of paralysis with 0.2 mg of sugammadex is administered and extubation is carried out after fulfilled criteria of extubation and TOF ratio monitoring of more than 90%. All patients are then transferred to the recovery room and monitored for 1.5 hours prior to transfer to ward.

For management of mechanical ventilation, all patients are ventilated by an anesthetic machine (Aespire View, Datex-Ohmeda Inc., Wisconsin, USA) with preset tidal volume of 8 mL/kg of predicted body weight, inspiratory to expiratory time ratio of 1:2 with 45% inspiratory pause, respiratory rate adjusted to maintain end-tidal carbon dioxide (EtCO₂) between 35 and 45 mm Hg, fraction of inspired oxygen (FiO₂) of 0.40 in one liter per minute of the mixture of oxygen and air which can be adjusted to maintain peripheral oxygen saturation (SpO₂) of equal or more than 95% and PEEP set according to the study groups. All included patients are randomly allocated into 2 groups, the control group (Group C) and the intervention group (Group E), by computer-generated block-of-four randomization. In the Group E, the 5-French, latex-free adult esophageal balloon catheter (CooperSurgical Inc., Connecticut, USA) is inserted after induction and intubation and connected to the pressure transducer system (TruWave, Edwards

Lifesciences, Irvine, USA). The proper position of the catheter is in the lower one third of the esophagus, which is determined by rising in pressure during positive pressure ventilation plus presence of cardiac oscillation recognized on the pressure tracing⁽¹⁸⁻²⁰⁾. The esophageal pressure (P_{eso}) is measured and used as a surrogate of P_{pl} ⁽¹⁹⁻²¹⁾. PEEP is titrated to maintain P_{TP} during expiration, which is equal to PEEP minus P_{eso} during expiration, between 0 and 5 cm H₂O. The conversion factor of 1.36 is used to convert mm Hg to cm H₂O. In the group C, the esophageal balloon catheter is inserted as in the group E for measuring P_{eso} but patients are ventilated with fixed PEEP of 5 cm H₂O throughout the operation.

Data collection

In all patients, demographic data including age, weight, height, body mass index (BMI), the ASA physical status, comorbid diseases, diagnosis, operation, duration of the operation are recorded. After induction and intubation and insertion of the esophageal balloon catheter, hemodynamic parameters including blood pressure, heart rate, cardiac index and stroke volume index; respiratory mechanics including peak inspiratory pressure, plateau pressure (P_{plat}), PEEP, P_{eso} during inspiration and expiration, and tidal volume; and gas exchange parameters including partial pressure of arterial oxygen (PaO₂) and carbon dioxide (PaCO₂), pH, FiO₂, SpO₂ and EtCO₂ are recorded as baseline T0 parameters. After initiation of PP and position in 45-degree Trendelenburg position, PEEP is set according to patient's group allocation. Hemodynamic parameters, respiratory mechanics, gas exchange parameters and IAP are recorded at 15 minutes and at one hour after setting of PEEP as T1 and T2 parameters, respectively. Thirty minutes after arrival in the recovery room, hemodynamic and gas exchange parameters are

recorded again as T3 parameters. The C_{RS} is calculated from tidal volume in mL divided by difference between P_{plat} and PEEP in cm H₂O and the alveolar dead space to tidal volume ratio (V_D/V_T) is calculated using the formula reported by Hardman et al⁽²²⁾. Adverse respiratory events defined as requirement of oxygen supplement after discharge from the recovery room, episodes of desaturation (SpO₂ of less than 90%), new-onset respiratory infection, new infiltration on chest radiograph, or respiratory failure are followed up in all patients for 72 hours postoperatively or until discharge from hospital. Length of hospital stay as well as other adverse events are also recorded.

Statistical analysis

The primary endpoint of the study is to determine the difference in oxygenation that is PaO₂ between the Group E and the Group C. Spadaro et al⁽¹⁵⁾ reported PaO₂ of 127.5±30 mm Hg during PP in patients undergoing laparoscopic abdominal surgery with application of PEEP of 5 cm H₂O. Meanwhile, PaO₂ was reported as high as 142.5±30 mm Hg⁽¹⁵⁾ to 190.2±11.9 mm Hg⁽¹²⁾ during PP with application of PEEP of 10 cm H₂O. Given that PaO₂ in the Group C is equal to that reported by Spadaro et al⁽¹⁵⁾ and estimated 20% higher PaO₂ in the Group E is clinically relevant, with a power of 0.8 and a significance level of 0.05, sample size of 22 subjects per group is required. The secondary endpoints are the difference in C_{RS} and V_D/V_T between the two groups, changes in hemodynamic parameters with application of PEEP, proportion of thoracoabdominal transmission of IAP as well as adverse respiratory events and length of hospital stay in the two groups.

Categorical variables are reported as number with percentage and compared between the groups using the chi-squared test or the Fisher's exact test as appropriated.

Continuous variables are tested for normal distribution with the Kolmogorov–Smirnov test and reported as mean with standard variation (SD) or median with interquartile range (IQR) and compared between the groups using the unpaired Student's t-test or the Mann Whitney U test as appropriated. The changes in parameters within the group are analyzed using the repeated-measure analysis of variance (ANOVA). For all analyses, a two-tailed test is performed and a *p* value of less than 0.05 is considered statistical significance. The statistical analysis is carried out using the IBM SPSS Statistics 21 (IBM Corporation, New York, USA).

Reference

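### A fixed, disclosed block size of four with visible arms makes on average one third of assignments deducible, and no safeguard against selection at entry is described

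*Combined protocol and SAP*

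**What the plan says.** The Study protocol section states that patients are allocated to two groups "by computer-generated block-of-four randomization". One block size is given, it is printed in the protocol, and no strata are described. The 1:1 ratio is not written out, but it follows from blocks of four and equal group sizes ("sample size of 22 subjects per group is required").

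The esophageal catheter is placed in both groups. PEEP is titrated against the esophageal reading in Group E and fixed at 5 cm H₂O in Group C, so whoever runs the ventilator knows that patient's arm. The Data collection section puts this step after baseline: "After initiation of PP and position in 45-degree Trendelenburg position, PEEP is set according to" the allocated group.

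Under Patient population, exclusions include "those with significant cardiovascular or respiratory diseases", with no definition of significant. Inclusion depends on an anticipated surgical duration of more than 2 hours.

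Under Statistical analysis, groups are compared by unpaired t-test or Mann-Whitney test. PaO₂ is recorded at T0, but no adjustment for it is planned.

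The available text does not say who generates or holds the list, how it is concealed, who enrols, when randomization happens relative to consent, or whether anyone is blinded.

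**The concern.** With a known block size of four, two or three visible allocations in a block can settle the rest. An enroller who can foresee the next arm, and who has discretion over eligibility, can influence which patient fills it, knowingly or not. Hiding the list does not prevent this, because the prediction comes from past allocations that have already been seen.

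PaO₂ is a laboratory measurement. That limits biased assessment, but not a difference in the patients entered. With no baseline adjustment, a shift in oxygenation at entry passes directly into the primary comparison and raises its type I error. In a trial of 44 patients a modest shift is not small relative to the planned difference.

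**Working it through.** **Inputs.** From Statistical analysis: control PaO₂ ("reported PaO₂ of 127.5±30 mm Hg during PP"), hence SD 30; a 20% difference; "with a power of 0.8 and a significance level of 0.05"; "a two-tailed test is performed"; 22 per group. From Study protocol: blocks of four. The size of any steering is not in the documents and is assumed below.

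**The plan's own figure.** Difference = 0.20 × 127.5 = 25.5 mm Hg. By the normal approximation, n = 2 × [30 × (1.960 + 0.842) / 25.5]² = 21.7, so 22 per group. This reproduces the plan. 44 patients make 11 complete blocks.

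**Certain assignments.** The six orders of a 2:2 block are EECC, CCEE, ECEC, ECCE, CEEC and CECE. In the first two, the last two assignments are forced; in the other four, only the last is.

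- Mean forced per block: (2×2 + 4×1)/6 = 4/3, or 33.3%.
- Over 11 blocks: 14.7 of 44, with a range of 11 (25%) to 22 (50%).

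**Guessable assignments.** The chance of a correct best guess at positions 1 to 4 is 1/2, 2/3, 2/3 and 1. The mean is 2.833/4 = 70.8%, against 50% by chance.

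**Other lists.**

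- One permuted 22:22 list: certain 2×22/23 = 1.9 of 44 (4%); correct guesses 22 + (2⁴⁴/C(44,22) − 1)/2 = 25.7 of 44 (58%).
- Randomly mixed blocks of 4 and 6 (simulated): about 5% certain, about 69% guessable.
- Randomly mixed blocks of 4, 6 and 8 (simulated): about 2% certain, about 68% guessable.

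**Bias under assumed steering.** Suppose there is no true effect, and a patient chosen for an expected E slot has PaO₂ higher by s, and one chosen for an expected C slot lower by s. Patients picked for E and for C then differ by 2s.

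- Acting only on certain assignments, blocks of four: 4/3 steered patients per block, 2 patients per arm, so bias = (4/3)/2 × s = 0.667s.
- Acting on every better-than-even guess, blocks of four: correct minus wrong guesses per block = 1/3 + 1/3 + 1 = 5/3, so bias = (5/3)/2 × s = 0.833s.
- Acting on every better-than-even guess, one 22:22 list: (2×25.68 − 44)/22 × s = 0.335s.

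The two-sided type I error of the t-test was simulated with SD 30.

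| s (gap 2s), mm Hg | Blocks of 4, certain only: bias; type I | Blocks of 4, best guess: bias; type I | One list, best guess: bias; type I |
|---|---|---|---|
| 3 (6) | 2.0; 0.05–0.06 | 2.5; 0.06 | 1.0; 0.05 |
| 7.5 (15) | 5.0; 0.08–0.09 | 6.3; 0.10 | 2.5; 0.06 |
| 15 (30) | 10.0; 0.18 | 12.5; 0.24–0.25 | 5.0; 0.07–0.08 |

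Against the planned 25.5 mm Hg, the blocks-of-four biases run from 2.0/25.5 = 8% to 12.5/25.5 = 49%.

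**The case against.** Block-of-four randomization is a valid method and contradicts nothing else in the plan. The route to bias also needs facts that the documents do not give.

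- **Who sees what.** The text shows that whoever sets PEEP in a case knows that case's arm. It does not show that one person sees all 44 allocations in order and tracks block starts, or that enrollers see earlier arms. A single centre is inferred from one named affiliation. Part of the document was not available, so a concealment statement there cannot be ruled out. This objection stands and limits the conclusion to a risk.
- **Can anyone steer?** The arterial line is placed after induction, so the study supplies no PaO₂ when a patient is enrolled. Patients of ASA status 3 or above and those with significant cardiorespiratory disease are excluded, which narrows the visible range. If a preoperative predictor correlated 0.3 with PaO₂ (assumed), shifting PaO₂ by 0.25 SD would need a predictor shift of 0.25/0.3 = 0.83 SD, or roughly half of candidates turned away at each steered slot. This makes the larger rows of the table less plausible. At s = 3 mm Hg the effect on type I error is slight.
- **T0 would show a gross imbalance.** It might, but the planned test would not correct for it.
- **Small blocks protect balance over calendar time,** for example while the team learns balloon-guided titration. This is fair, but no strata, sites or interim looks are described that would require blocks as small as four.

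A reader might infer that the primary comparison is biased, or that recruiters will know a third of the allocations in advance. The documents support neither reading, since both depend on the unstated facts above. A reader might also infer that small mixed blocks achieve nothing. They do remove most of the certainty, but little of the better-than-chance guessing.

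**Conclusion.** The point holds as an uncontrolled risk of selection at entry. Following the stated rule produces a list that is predictable to anyone who knows the block size and follows earlier allocations: on average 33% certain (25% to 50% in a given sequence) and 71% guessable, against 4% and 58% for one permuted list. These figures are exact for such an observer. Whether such an observer enrols patients is not stated.

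The bias and type I error figures illustrate assumed steering and do not estimate what will happen. Within the assumed range, blocks of four give 2 to 12.5 mm Hg of bias and type I error from just above 0.05 to about 0.25. One list gives 1 to 5 mm Hg and at most about 0.08 under the same best-guess steering. The change is worth making because it is cheap and nothing described in the design depends on the small fixed block.

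**What to change.** 1. Replace the block-of-four wording with one randomly permuted list of 22 E and 22 C, with extra slots generated in advance in case patients excluded for short surgery are replaced. Alternatively, use large, randomly varying blocks whose sizes are kept out of the protocol and away from recruiters. Mixed blocks of 4 and 6 are a weaker option: certainty falls to about 5%, but about 69% stays guessable.
2. State who generates and holds the list and who enrols, and keep enrolment separate from those who see the arms where possible.
3. Reveal each allocation only after the patient is irrevocably enrolled. After T0 is recorded would be a natural moment, but the plan must first be reconciled on when group-specific PEEP starts: the Study protocol section has Group C on its fixed PEEP for the whole operation, while Data collection sets PEEP by group only after pneumoperitoneum and positioning. Late reveal supports concealment but does not stop prediction from past allocations, so it does not replace step 1.

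The cost is a small change to list generation and a few sentences of protocol text. The downside is slightly less balance over calendar time, or in group sizes if recruitment stops early.

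### The primary PaO₂ comparison names no time point or summary, so at least two unadjusted tests can each claim to be the primary result

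*Combined protocol and SAP*

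**What the plan says.** All references are to the combined protocol and SAP.

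- **Endpoint.** Statistical analysis states the primary aim as "to determine the difference in oxygenation that is PaO₂ between the Group E and the Group C". It names no time point, change score, average or success rule.
- **Measurements.** Under Data collection, PaO₂ is one of the gas exchange parameters. The first set, taken after intubation and catheter insertion, "are recorded as baseline T0 parameters". After pneumoperitoneum (PP) and head-down positioning, PEEP is set by allocation, and the same parameters "are recorded at 15 minutes and at one hour after setting of PEEP as T1 and T2 parameters, respectively". T3 follows: "Thirty minutes after arrival in the recovery room, hemodynamic and gas exchange parameters are" recorded again.
- **Tests.** Between-group comparisons of continuous variables use the unpaired t-test or the Mann–Whitney test. Repeated-measures ANOVA is reserved for changes within a group. All tests are two-sided, and a p "value of less than 0.05 is considered statistical significance". No multiplicity adjustment is mentioned.
- **Sample size.** The control value comes from an earlier study that "reported PaO₂ of 127.5±30 mm Hg during PP in patients undergoing laparoscopic abdominal surgery with application of PEEP of 5 cm H₂O". A 20% higher value in Group E, 80% power and a 0.05 level give 22 per group.
- **Secondary endpoints.** The list contains no PaO₂ time point, so the primary one cannot be found by elimination.

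**The concern.** PaO₂ is measured three times after the intervention starts, and the primary endpoint does not choose among them. The words *during PP* in the sample-size paragraph describe earlier studies. They fit T1 and T2 equally and do not fit T3. Because the ANOVA is confined to within-group change, it supplies no single between-group test across time. Following the plan as written therefore produces separate t-tests or Mann–Whitney tests at each time, each at 0.05, for a claim sized as one comparison.

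If T1 is significant and T2 is not, or the reverse, the plan cannot say whether the trial met its primary endpoint. The choice could then be made after the results are known.

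**Working it through.** **1. Reproduce the stated sample size.** Inputs from Statistical analysis: control mean 127.5 mm Hg, SD 30, difference 0.20 × 127.5 = 25.5 mm Hg, two-sided 0.05, power 0.80.

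n per group = 2 × (1.960 + 0.842)² × 30² / 25.5² = 21.7, rounded up to **22**. This matches the plan, and it is the size for a single comparison. Power at 22 per group is 80.5% by the normal approximation and 78.6% by the exact noncentral t (42 degrees of freedom).

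**2. Assumptions for the two-time-point question.** The documents give neither a success rule nor a correlation between T1 and T2. I took correlations r from 0.5 to 0.95, normal outcomes with equal SD, 22 per group, and an unpaired t-test at two-sided 0.05 (critical value 2.018). For the planned effect I assumed 25.5 mm Hg at both T1 and T2.

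**3. Results** (simulation, 400,000 trials per setting):

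| r | No effect: either significant | No effect: both significant | Planned effect: either | Planned effect: both | Planned effect: exactly one |
|---|---|---|---|---|---|
| 0.5 | 9.2% | 0.9% | 90.5% | 66.6% | 23.9% |
| 0.7 | 8.4% | 1.6% | 87.9% | 69.5% | 18.4% |
| 0.8 | 7.8% | 2.1% | 86.2% | 71.0% | 15.2% |
| 0.9 | 7.1% | 2.9% | 83.9% | 73.3% | 10.6% |
| 0.95 | 6.5% | 3.5% | 82.4% | 74.9% | 7.5% |

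With one time point fixed in advance, the corresponding figures are 5% and 78.6%.

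Checks: bivariate normal probabilities for the either rule with no effect are 9.1% at r = 0.5, 7.0% at 0.9 and 6.5% at 0.95. The ceiling for two independent tests is 1 − 0.95² = 9.75%.

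**4. If T3 could also count** (any of three significant, no effect, equal correlations): about 12.6% at r = 0.5, 10.9% at 0.7, 10.0% at 0.8, 8.4% at 0.9 and 7.4% at 0.95.

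**5. Would a T1/T2 mean keep the power?** The SD of a patient's mean of T1 and T2 is 30 × √((1 + r)/2), which is 26.0 at r = 0.5 and 29.6 at r = 0.95. Noncentral-t power at 22 per group, without T0 adjustment, is:

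| r | 0.5 | 0.7 | 0.8 | 0.9 | 0.95 |
|---|---|---|---|---|---|
| Power | 88.9% | 84.8% | 82.7% | 80.7% | 79.7% |

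Each value is above the 78.6% for a single time point.

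**The case against.** The strongest reply is that the plan never says significance at either time is enough. The 6.5–9% belongs to a rule supplied from outside. A both-times rule would give 0.9–3.5%, and a single fixed time 5%. That is correct. What the documents establish is that the error rate is undefined. The inflation is conditional.

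Other points, and what stands of each:

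- **T3.** The sample-size paragraph and the stated aim both concern ventilation during surgery, and T3 is taken after extubation. The practical ambiguity is T1 against T2, and the three-time-point figures should carry little weight.
- **Correlation.** T1 and T2 are 45 minutes apart in the same ventilated patient, so a high correlation is plausible, though not documented. At 0.9–0.95 the excess over 5% is only about 1.5–2 percentage points.
- **Disagreement.** Here it means one p-value below 0.05 and one above. In over 99% of such simulated trials the two effects point the same way, and the median non-significant p-value is about 0.07–0.11. The figure reflects a threshold crossed at one time and missed at the other, not contradictory evidence. It does show how often the verdict would depend on an unstated choice. Unequal effects can raise it: about 32% at r = 0.8 with standardised effects of 0.6 and 0.85.
- **T0 as covariate.** Study protocol gives Group C a fixed PEEP for the whole operation and does not state Group E's PEEP at T0. If the groups already differed at T0, adjustment could remove part of the effect. Data collection places the allocated setting after T0, so T0 is usable as a baseline on that reading, but the two sections should be reconciled on this point.

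None of these identifies the primary time point.

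**Conclusion.** The concern holds and must be fixed. The trial's only primary endpoint has no time point, summary or success rule, and this finding needs no assumption.

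The size is conditional. The false-positive rate of about 6.5–9% requires an either-time rule and a correlation of 0.95–0.5. The 8–24% of trials with exactly one significant result (7.5–23.9% before rounding) also requires the planned 25.5 mm Hg effect at both T1 and T2. Power likewise depends on the unstated rule: 82–91% under either, 67–75% under both, 78.6% for one fixed time. Confidence is high for the omission; the rates are only as good as the assumed correlation.

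**What to change.** Before any data are seen, name one primary between-group PaO₂ comparison during PP and test only that at 0.05.

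- **Option A:** choose T1 or T2. T2 is a reasonable choice, though nothing in the sample-size wording singles it out. This takes one sentence and leaves the sample-size calculation as it is.
- **Option B:** use each patient's mean of T1 and T2 PaO₂, compared between groups in a linear model with T0 PaO₂ as covariate. This needs a short model specification in place of the t-test or Mann–Whitney choice for the primary analysis, and a statement that T0 is recorded before PEEP differs by group.

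List the remaining PaO₂ time points, including T3, as secondary.

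Neither option needs extra patients or samples. The price is that a difference seen only at another time becomes a secondary result, and that averaging under Option B dilutes an effect present at only one of T1 and T2.

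### Several components of the adverse respiratory event endpoint depend on postoperative staff decisions, and nothing ensures that those who make or record them are unaware of the arm, so detection can differ by group

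*Combined protocol and SAP*

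**What the plan says.** The Data collection section defines adverse respiratory events by five components. Two of them are "requirement of oxygen supplement after discharge from the recovery room, episodes of desaturation", the latter with a threshold of SpO2 below 90%. The others are "new-onset respiratory infection, new infiltration on chest radiograph, or respiratory failure". These events "are followed up in all patients for 72 hours postoperatively or until discharge from hospital". The Statistical analysis section lists "adverse respiratory events and length of hospital stay in the two groups" among the secondary endpoints and compares categorical variables by the chi-squared or Fisher's exact test.

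Patients are allocated "by computer-generated block-of-four randomization". After pneumoperitoneum and positioning, "PEEP is set according to patient's group allocation": in Group E it is titrated to the esophageal pressure, while Group C "patients are ventilated with fixed PEEP of 5 cm H₂O throughout the operation". The esophageal catheter is placed in both groups; in Group C its stated purpose is measurement. Under Study protocol, patients are monitored for 1.5 hours in the recovery room before going to the ward.

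The available text does not mention blinding of patients, recovery or ward staff, radiograph readers or outcome assessors, and does not say who records the 72-hour events.

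**The concern.** Three of the five components are recorded only if someone acts. Ward oxygen is a treatment decision with no stated criterion. Desaturation on the ward is found only when SpO2 is measured, and oxygen already running can hide it. A new infiltrate needs a film, and none is scheduled.

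Whoever sets PEEP has to know the arm. Recovery and ward staff have no such need, yet the plan neither keeps the allocation from them nor says that the recorder of events is someone who does not know it. If knowledge of the arm reached them, their expectations could change how readily oxygen is given, SpO2 is checked or a film is ordered. Belief that titrated PEEP protects the lung would lower detection in Group E; worry about higher PEEP would raise it. The test compares recorded events and cannot separate a difference in risk from a difference in detection. Apart from length of stay, these events are the only clinical outcome among the listed endpoints.

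**Working it through.** **1. The plan's own figure.** The sample size concerns PaO2 only. The inputs, from Statistical analysis, are a control mean of 127.5 mm Hg, SD 30, a 20% increase, power 0.8 and two-sided alpha 0.05. The difference is 0.20 × 127.5 = 25.5 mm Hg. The normal formula gives n = 2 × (1.960 + 0.842)² × 30² / 25.5² = 21.7, so 22 per group, as stated. The event endpoint has no planning figure. What carries over is the group size: one patient is 1/22 = 4.5 percentage points.

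**2. Who generates each component, on the text.**

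| Component | What makes it appear | What the plan standardises |
|---|---|---|
| Oxygen after recovery-room discharge | A decision to give it | Nothing stated |
| Desaturation | A measurement of SpO2 | Threshold below 90%; 1.5 hours of recovery-room monitoring; no ward check times |
| New infiltrate | A radiograph | No film scheduled, no rule for taking one |
| Infection, respiratory failure | A diagnosis | No criteria stated; the point does not rest on these |

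The follow-up window is the same in both arms, but an equal window does not make checking within it equal.

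**3. Illustration of size. Every event and detection rate here is an assumption.** Let the true risk p be the same in both arms, and let d be the share of events detected. The recorded risk is p × d, so the apparent risk ratio (E/C) is d_E / d_C whatever p is. With n = 22 per group:

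| Detection C / E | Recorded risk at p = 20% | Expected events at p = 20% | Apparent ratio E/C | Difference for p = 10% to 40% | Chance of Fisher p < 0.05 at p = 20% (range for p = 10% to 40%) |
|---|---|---|---|---|---|
| 100% / 100% | 20% v 20% | 4.4 v 4.4 | 1.00 | 0 | 2.4% (1.4% to 2.4%) |
| 90% / 70% | 18% v 14% | 4.0 v 3.1 | 0.78 | 2 to 8 points | 3.1% (1.2% to 4.6%) |
| 90% / 50% | 18% v 10% | 4.0 v 2.2 | 0.56 | 4 to 16 points | 6.1% (1.5% to 13.9%) |

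The last two rows put the lower detection in Group E. With the arms swapped, the ratios become 0.9/0.7 = 1.29 and 0.9/0.5 = 1.80. The differences change sign, and the last column is unchanged because the groups are equal in size.

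**4. Extra recording instead of missed events (also assumed).** If three patients in one arm are recorded only because of discretionary oxygen or films, the groups differ by 3/22 = 13.6 points with no true effect. If those are the only events, 3/22 against 0/22 gives a two-sided Fisher p of 2 × C(22,3)/C(44,3) = 2 × 1,540/13,244 = 0.23.

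**The case against.** The strongest reply is that the documents do not show that anyone on the ward knows the arm. PEEP is an intraoperative ventilator setting that ends at extubation, and the catheter goes into both groups, so it does not reveal the allocation. Recovery and ward staff may well be unaware in practice. A reader might infer that the allocation travels with the anesthetic record at handover. The text describes no handover and does not say what that record contains or who sees it, so this cannot be asserted. What stands against the reply is that nothing ensures unawareness either, and an unstated safeguard cannot be verified or reported.

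A reader might also infer that the whole endpoint is a matter of staff judgment. That goes too far. Desaturation has a numeric threshold, and all patients are monitored for 1.5 hours in the recovery room, so the SpO2 concern applies mainly to the ward.

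Finally, the endpoint is one of several secondary ones, and the trial is sized for a blood-gas measurement. That limits the consequence but does not remove it.

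**Conclusion.** The point holds as a possibility that the plan leaves open, not as a demonstrated bias. Three components depend on staff decisions, and the available text does not keep the people who make or record those decisions unaware of the arm. Part of the document was not available for review, so the conclusion covers only the text seen.

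The main risk is a distorted estimate. Under the assumed detection gaps the apparent risk ratio moves from 1.00 to 0.78 or 0.56, or to 1.29 or 1.80 in the other direction. A reader might infer that false significance is likely. The calculation does not support that: the chance of Fisher p < 0.05 stays below 5% in most of the cases tried, and exceeds it only when the gap is 90% against 50% and the true risk is 20% or more. Nor do the documents support any one direction of bias. Primary PaO2 is not affected by this route. This is a worthwhile, inexpensive improvement to a secondary comparison.

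**What to change.** - State that group allocation is kept on the study form and not communicated to recovery or ward staff, with disclosure allowed for clinical need.
- Have the 72-hour events recorded by existing staff who were not in the intraoperative team and are not told the arm. This is feasible because both groups receive the catheter.
- Report each component separately by group, together with the number of patients in each group who had a radiograph, so that unequal detection is visible.

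The clinical record stays as it is, so masking may be incomplete if someone infers the arm from it. The component and radiograph counts would help to show any resulting difference in detection. The cost is protocol wording, a little more data handling and a disclosure route to maintain. Sample size and treatment do not change.
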